#### 1-week, 3-month, and 6-month Follow-up Assessments

When we enroll patients in the study we will schedule the 1-week follow-up (we allow up to 3 weeks after their scheduled follow-up to contact the patient). This is scheduled one week from the expected date of receipt of the intervention materials. If the patient did not receive the intervention materials, we re-send them and re-schedule the 1-week follow-up. The 3- and 6-month follow-ups are triggered by completion of prior follow-ups.

We will request contact information from patients at the time of enrollment. We will ask for names and contact information of additional persons who might be able to locate the patient if we cannot. During the 1-week follow-up assessment interview, we will administer the main outcome measures for the study (Preparation for Decision Making Scale, Decisional Conflict Scale), the secondary outcome measures (knowledge, screening intentions), and the measures of acceptability of the materials. See appendix M for the 1-week follow up survey. At the 3-month and 6-month follow-up assessments (we have up to three weeks after their scheduled follow-up date to contact the patients),

we will repeat the knowledge measure and ask about any use of lung cancer screening services. See appendices N and O for the 3-month and 6-month follow-up surveys, respectively.

If we are not able to complete the follow-up interviews by phone, we will mail a study questionnaire to the patient at the address they provide. Patients will receive \$50 after completion of the 1-week assessment and \$25 after completion of the 3-month assessment in the form of gift cards mailed to them (\$75 total). Patients asked to do the 6-month assessment will be mailed an additional \$25 gift card when they complete it. Subject compensation will be tracked in a log (see appendix P).

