#### Analysis plan

Patients' demographic characteristics at baseline will be summarized using descriptive statistics such as mean, standard deviation, median, interquartile range (IQR), and frequency where appropriate. We will apply Student t-test/Wilcoxon test and Kruskal-Wallis test/analysis of variance (ANOVA) to compare continuous variables between arms, and the chi-square test or the Fisher's exact test to assess the differences of categorical variables between arms.[16]

As primary analysis, we will perform two-sided two group t-test to compare the differences of the three primary endpoints between the two arms. We will perform similar analysis on knowledge scores. For these efficacy endpoints, intend-to-treat analysis will be applied to the participants. We will look at the impact of race/ethnicity (African American vs. Caucasian) on the relationship between the outcomes and lung cancer screening materials using general linear regression. We will also assess the interaction between intervention and race/ethnicity using linear regression model to examine whether or not the decision aid has differential effects between African Americans and Caucasians by testing.

We will use two-sided two group t-test to compare the change of knowledge scores from baseline to post intervention between the two arms. Since the knowledge outcome will be assessed at week 1 and then 3-month and 6-month follow-ups, linear mixed effect models for longitudinal measures[17] will be employed to assess the change in the magnitude of the outcomes over time adjusting for multiple covariates including intervention indicator, age, gender, race, education level, insurance status, and other factors. We may also look at the interaction between intervention and time. Appropriate transformation of the measures will be used in the analyses to satisfy the normality assumption of linear mixed effect model. Mode of administration and completion of intervention/control materials (i.e., dose/exposure) will be tracked to account for their

effects.

We will also estimate the lung cancer screening rate within each arm along with 95% confidence interval. Chi-square test will be used to assess the differences of the lung cancer screening rates between arms.

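### The 3- and 6-month follow-ups are triggered by completing the previous one, which adds avoidable selection and timing spread to later knowledge and screening outcomes

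*Combined protocol and SAP*

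**What the plan says.** All the scheduling rules are in section 4.0 of the combined protocol and SAP, under the heading on the 1-week, 3-month and 6-month follow-up assessments.

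- The 1-week contact has its own anchor: "This is scheduled one week from the expected date of receipt of the intervention materials". The contact window is stated as "we allow up to 3 weeks after their scheduled follow-up to contact the patient". Non-delivery is handled as follows: "If the patient did not receive the intervention materials, we re-send them and re-schedule the 1-week follow-up".
- The later contacts have no anchor of their own: "The 3- and 6-month follow-ups are triggered by completion of prior follow-ups". Each has its own allowance: "we have up to three weeks after their scheduled follow-up date to contact the patients".
- At the later contacts, "we will repeat the knowledge measure and ask about any use of lung cancer screening services".
- There is a back-up mode: "If we are not able to complete the follow-up interviews by phone, we will mail a study questionnaire to the patient". Patients are also asked at enrolment for other people who could help locate them.

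The opening of section 4.0 limits the 6-month contact to a subsample, and section 5.0 expects about 300 patients (150 per arm) to complete it. In the Analysis plan, after the sentences on the three primary endpoints and knowledge, the text reads: "For these efficacy endpoints, intend-to-treat analysis will be applied to the participants". Knowledge over time is analysed with a linear mixed model, and screening rates with a chi-square test. The plan names no method for missing data and does not use actual elapsed time.

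**The concern.** Completing an assessment happens after randomisation. If it decides who is approached next, the patients with 3- and 6-month data are selected by something that could depend on arm. There is a plausible route: section 4.0 says the decision aid is a video that may need a DVD player, Internet access or a visit to a library, and a patient who has not yet watched it might put off the 1-week interview.

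The planned analyses do not repair this. A patient with no 1-week assessment and no later approach contributes no post-baseline knowledge score to the mixed model, only a pre-test made up of a subscale of the knowledge measure. In the chi-square test of screening, that patient is simply absent.

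Timing is the second issue. If the clock restarts at each completion, lateness accumulates and the nominal 6-month report covers different lengths of time for different patients. Screening accrues with time, and retention of knowledge also depends on the interval.

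**Working it through.** **The plan's own figure.** Section 5.0 gives 83% power for screening rates of 0.20 and 0.35 with 150 per arm and two-sided alpha 0.05. The formula is z = [d√n − 1.96√(2p̄(1−p̄))] / √(p₁(1−p₁) + p₂(1−p₂)), with d = 0.15 and p̄ = 0.275.

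- z = (0.15 × 12.247 − 1.96 × 0.6315) / 0.6225 = 0.963, so power is 0.832. The stated 83% reproduces.
- It stays valid if 300 patients do complete the 6-month contact. Power would be 78% at 130 per arm and 86% at 160.

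**Patients with no route to later contacts.** The documents give 550 recruited and 80% retention by 3 months, but no 1-week completion rate. I assume 80% to 95%.

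- 95%: 550 × 0.05 = 27.5, about 28 patients.
- 80%: 550 × 0.20 = 110 patients. This is the extreme case, in which all the planned 3-month loss has already occurred at 1 week.
- Planned 3-month number: 550 × 0.80 = 440. If half of those without a 1-week assessment could still be reached, it would rise to 440 + 13.75 ≈ 454, or to 440 + 55 = 495. The half is also an assumption.

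**Timing.** Weeks are counted from expected receipt of materials. Three months is taken as 13 weeks, and each chained interval is assumed to run from actual completion of the previous contact.

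| Contact | Chained, earliest | Chained, latest | Fixed date, same 3-week window |
|---|---|---|---|
| 1-week | 1 | 1 + 3 = 4 | 1 to 4 |
| 3-month | 1 + 13 = 14 | 4 + 13 + 3 = 20 | 13 to 16 |
| 6-month | 14 + 13 = 27 | 20 + 13 + 3 = 36 | 26 to 29 |

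The 6-month spread is 9 weeks chained and 3 weeks fixed, so chaining adds 9 − 3 = 6 weeks. At 3 months it adds 6 − 3 = 3 weeks. Re-sent materials and mailed replies, for which no time limit is stated, would add more.

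**Effect on screening rates.** Assume a constant hazard that gives the plan's rates at week 26: λ = −ln(1 − p)/26, and cumulative rate 1 − exp(−λt).

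| | Week 26 | Week 27 | Week 29 | Week 36 |
|---|---|---|---|---|
| Standard materials | 20.0% | 20.7% | 22.0% | 26.6% |
| Decision aid | 35.0% | 36.1% | 38.2% | 44.9% |

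As an outer bound, suppose both arms had the lower hazard, but every patient in one arm was seen at week 27 and every patient in the other at week 36. The spurious difference would be 26.6 − 20.7 = 5.9 percentage points. If lateness is the same in both arms, equal hazards give equal rates and no spurious difference.

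**The case against.** Four stronger readings are tempting, and the documents support none of them.

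- **One missed call ends follow-up.** A reader might infer this from the trigger sentence alone. The same section gives a 3-week window, locator contacts and a mailed questionnaire, so a patient leaves the chain only when both phone and mail fail. Such patients are also harder to reach later, so the recoverable number is unknown. Nor does the text say that non-completers are never contacted; it simply gives no other route.
- **The planned attrition measures the harm.** The loss implied by section 5.0 is 550 × 0.20 = 110 patients, or 550 − 400 = 150 from the target final sample. Either figure is loss from all causes. It includes patients who completed 1 week, were properly approached at 3 months and did not respond.
- **Chaining adds 9 weeks, or 9/26 = 35% more time.** Three of those weeks are the 6-month contact's own window and would remain under fixed scheduling. The part due to chaining is at most 6/26 = 23%, and only for a patient at the limit of every window.
- **The arm comparison is biased and intention to treat is broken.** The same rule applies to both arms, and nothing in the documents shows that lateness or non-completion differs between them. Re-scheduling is for materials not received, not for materials not viewed. The Analysis plan tracks completion of the materials as exposure, which suggests that viewing is recorded rather than required for the interview. The intention-to-treat sentence follows the primary endpoints and knowledge; screening is treated separately, and section 2.0 calls it exploratory. The mixed model can use 1-week knowledge from patients lost later.

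These answers limit the size and reach of the point. They do not supply the missing route for a reachable patient who did not complete an earlier assessment, and they do not bring elapsed time into the screening analysis.

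**Conclusion.** The point holds for the later outcomes only. The rule as written makes the approach at 3 and 6 months conditional on a post-randomisation event, with no stated alternative, and it lets contact times spread further than the windows require. It affects 3- and 6-month knowledge and screening completion. The chain does not touch the primary comparison: a patient without a 1-week assessment lacks the primary outcomes because that assessment is missing, not because of what follows it.

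The number of patients lost through the rule is unknown, and 28 to 110 of 550 is a range that rests on the assumed completion rate. The added spread of up to 6 weeks at 6 months depends on reading the trigger as also restarting the clock, which is natural but not spelled out. Differential selection or lateness by arm is plausible but not shown. Without it, the timing issue blurs what a 6-month rate means rather than biasing the comparison. The change is worth making because it is cheap and removes the question.

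**What to change.** Replace the trigger sentence in section 4.0 with three rules:

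1. Schedule the 3- and 6-month follow-ups from one fixed date for every patient, either randomisation or expected receipt of materials, keeping the existing windows.
2. Attempt each follow-up that is due, by phone and then mail, whether or not earlier ones were completed, unless the patient withdraws. For 6 months, this applies to the patients in the planned subsample.
3. Record the actual time from the fixed date to each completed assessment. In the Analysis plan, use it in the screening comparison, at least as a sensitivity analysis.

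If the sponsor already intends to contact everyone, one sentence saying so covers the second rule.

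The cost is wording plus extra calls, mailings and gift cards for the minority who missed an earlier assessment. At $25 each, the 3-month cards would cost at most 28 × $25 = $700 to 110 × $25 = $2,750 over the assumed range, if every such patient then responded, with a further $25 for each one who completes 6 months. There is one trade-off: with a date fixed at randomisation or the first mailing, patients whose materials were re-sent have a somewhat shorter interval over which retention of knowledge is measured. The recorded times would show how many are affected.

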## **5.0 Statistics and Justification of Sample Size**

### Justification of Sample Size

The primary analysis will be to compare three primary outcomes, i.e., Preparation for Decision Making Scale, informed subscale (IS) and values subscale (VS) of Decisional Conflict Scale (DCS), between patients who were randomized to the patient decision aid arm (Arm 1) and those who were randomized to the standard educational materials (Arm 2). We specifically chose the IS and VS subscales because two of the International Patient Decision Aid Standards criteria for decision aids are that the aid helps individuals feel informed and clear about values. Since the three primary endpoints are equally of significance, to control overall type I error rate at a significant level of 0.05, we will compare each of the three primary outcomes at a significant level of 0.017 (0.05/3) using Bonferroni multiple comparison adjustment.

Based on results from other decision aid trials using the DCS, we estimate Arm 2 will have a mean DCS IS or VS score of 30 while Arm 1 will have a mean DCS IS or VS of 25.[15] A sample size of 190 in each arm will have 80% power to detect a difference in means of 5 using a two group t-test with a 0.017 two-sided significance level assuming a common standard deviation (SD) of 15 on IS or VS.[15] We calculated the effect size the study would be able to detect with the given sample size for preparation for decision making because we had limited preliminary data for this measure. A sample size of 190 in each arm will have 80% power for the study to detect an effect size of 0.332 using a two group t-test with a 0.017 two sided significance level.

As a secondary analysis, we will also compare the difference of knowledge scores between the two arms using two-sided two group t-test. We hypothesize that Aim 2 scores to be 50 (half the knowledge questions answered correctly) with a SD of 19.36.[12] We further expect, based on our pilot study, the knowledge scores for Aim 1 to have a SD of 15.76.[12] If we randomize 380 participants 1:1 to each of the two arms, we would have 88% power to detect a difference in knowledge scores of 5.75 (50 vs. 55.75) using a two-sided two-sample t-test with unequal variances and alpha of 0.05. Therefore, the target final sample for the study will be 400 patients (200 per study arm). With an anticipated retention rate of 80% by the 3-month follow-up, 550 patients will be recruited for the study.

We will also estimate actual screening rate (ASR) for lung cancer within each arm and

compare the ASRs between the two arms. We expect that approximately 300 participants will complete the 6-month follow-up assessment and provide information about completion of lung cancer screening (150/arm). A two group chi-square test with a 0.05 two-sided significance level will have 83% power to detect the difference between a ASR of 0.2 in Arm 2 and a ASR of 0.35 in Arm 1 (odds ratio of 2.154) when the sample size in each arm is 150.

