## **2.0 Objectives**

This protocol addresses the second phase of a larger project funded by the Patient-Centered Outcomes Research Institute to help heavy smokers make informed decisions about lung cancer screening with low-dose computed tomography (LDCT).

This is an educational research study. Patients of state-based tobacco quitlines will receive educational materials about lung cancer screening to help them understand the potential benefits and harms of screening. This is not a study to evaluate the outcomes of screening for lung cancer.

Our quitline partners for this study are tobacco cessation counseling service providers who operate state-based quitlines as members of the North American Quitline Consortium. Patients for this study will therefore be quitline patients from participating states where these partners have contracts to provide services. This expands on our initial quitline partner, Information & Quality Healthcare (IQH).

The aim of this phase is to compare outcomes for promoting informed screening decisions about lung cancer screening in a randomized trial of patients who smoke recruited through state-based smoking cessation quitlines, where patients will be randomly assigned to the updated patient decision aid or to standard educational materials on lung cancer screening.

We will test several hypotheses related to the use of the patient decision aid in promoting informed decisions about lung cancer screening. Specifically, compared to heavy smokers who receive standard educational materials which lack an emphasis on making an informed decision, heavy smokers who view the patient decision aid about lung cancer screening will report:

1. being more prepared to make a decision about lung cancer screening,

2. feeling more informed about the screening decision, and
3. being clearer about their values related to the tradeoffs between benefits and risks of lung cancer screening with LDCT.

We further hypothesize that heavy smokers who view the decision aid will be more knowledgeable about lung cancer screening than patients receiving the standard educational materials. We will also collect data about screening intentions and completion of screening for exploratory purposes. We make no a priori hypotheses about these latter outcomes because the literature on the impact of decision aids on cancer screening uptake is mixed.

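### The Bonferroni rule for the three co-equal primary outcomes is valid, but pre-specifying Holm would control the same 0.05 error with more power per outcome and no extra patients

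*Combined protocol and SAP*

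**What the plan says.** Section 5.0 of the combined protocol and SAP, under Justification of Sample Size, names three primary outcomes: the Preparation for Decision Making Scale, and the informed (IS) and values (VS) subscales of the Decisional Conflict Scale. They carry equal weight ("Since the three primary endpoints are equally of significance"). The family-wise error is to be held at 0.05, and the rule for doing so is: "we will compare each of the three primary outcomes at a significant level of 0.017 (0.05/3) using Bonferroni multiple comparison adjustment".

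The power statements use the same level:

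- For IS and VS: "A sample size of 190 in each arm will have 80% power to detect a difference in means of 5". The calculation takes an SD of 15 in both arms and a two-sided t-test at 0.017.
- For Preparation for Decision Making the section gives only what 190 per arm could detect, "80% power for the study to detect an effect size of 0.332", because preliminary data were limited.
- The final target is 200 per arm.

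The Analysis plan in the same section repeats the two-sided t-tests on the three outcomes but gives no significance level and no multiplicity rule. No step-down procedure appears anywhere.

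Section 2.0 Objectives states hypotheses on all three outcomes. The claim is about what "heavy smokers who view the patient decision aid about lung cancer screening will report", and the list under it covers preparedness, feeling informed and clarity about values. The documents do not say whether success means one, some or all of them.

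**The concern.** Single-step Bonferroni tests every outcome at 0.05/3, whatever the other two show. Once one null hypothesis has been rejected, at most two true nulls can remain, and 0.05/3 is stricter than control of the family-wise error requires. Holm uses that slack: the ordered p-values are compared with 0.05/3, 0.05/2 and 0.05, stopping at the first that fails.

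The slack is largest when several effects are real, which is what the objectives hypothesise. Holm needs no assumption about correlation. It also treats the three outcomes symmetrically, so it respects their equal standing, as a fixed testing order would not.

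At stake is the chance of confirming the second and third hypotheses with the data the trial will collect anyway. Error control is not at stake.

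**Working it through.** **Inputs from the documents.** 190 per arm, 1:1 allocation, two-sided t-tests, difference 5 and SD 15 for IS and VS (5/15 = 0.333), detectable effect 0.332 for Preparation for Decision Making, level 0.017 written as 0.05/3, target 200 per arm.

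**Inputs assumed.** The documents give no correlation between outcomes, so 0 to 0.9 is used, equal for each pair, with all outcomes oriented so that benefit is positive. An effect of 1/3 is also assumed for Preparation for Decision Making in the main case, and smaller values are shown below.

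**Step 1: the plan's own figure.** With the normal approximation, n per arm = 2 × (SD/difference)² × (z for 1 − α/2 + z for power)².

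- At α = 0.017: 2 × 9 × (2.387 + 0.842)² = 187.6, so 188.
- At α = 0.05/3: 2 × 9 × (2.394 + 0.842)² = 188.4, so 189.
- Power at 190 per arm and effect 1/3, noncentral t: 80.2% at 0.017 and 80.0% at 0.05/3.
- Power at effect 0.332 and level 0.017, noncentral t: 79.9%.

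The plan's 190 per arm and 80% reproduce, and using 0.05/3 unrounded does not change the sample size.

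**Step 2: Bonferroni against Holm, all three effects 1/3.** Three correlated normal test statistics were simulated (1,000,000 draws per setting), each with mean effect × √(n/2) = (1/3) × √95 = 3.25. Bonferroni is at 0.05/3.

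| Correlation | Per outcome, Bonferroni | Per outcome, Holm | All three, Bonferroni | All three, Holm | At least one, either rule |
|---|---|---|---|---|---|
| 0 | 80% | 88% | 52% | 72% | 99% |
| 0.3 | 80% | 87% | 58% | 75% | 97% |
| 0.5 | 80% | 87% | 62% | 77% | 95% |
| 0.7 | 80% | 86% | 66% | 80% | 92% |
| 0.9 | 80% | 85% | 73% | 83% | 87% |

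The last column is the same for both rules because Holm's first step is the Bonferroni test.

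**Step 3: a smaller effect on Preparation for Decision Making** (IS and VS kept at 1/3, correlation 0 to 0.9).

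- Effect 0.2: IS and VS power rises from 80% to 82-86%. Preparation for Decision Making goes from 33% to 46-49%. All three goes from 21-33% to 39-49%.
- Effect 0: IS and VS power rises from 80% to 82-84%.
- If only one of the three outcomes has an effect, the gain on it is about 0.

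**Step 4: at the 200 per arm target**, all effects 1/3, correlation 0 to 0.9. Per outcome, 83% becomes 87-90%. All three goes from 56-75% to 76-85%.

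**The case against.** The strongest reply is that nothing is broken. The rule is pre-specified and valid, and the trial is sized at that level. Bonferroni also gives simultaneous confidence intervals that agree exactly with its decisions, which Holm does not. All of this stands, and it is why the point is an improvement only.

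A second reply is that the large gain, for showing all three, answers a question the plan never poses. This also stands in part. A reader might infer from the 52-73% that the quoted 80% is overstated. The documents do not support that: the 80% is stated per outcome, it is met, and success is nowhere defined as all three. If success means at least one, Holm adds nothing. What survives is the per-outcome gain, which needs no definition of overall success.

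A third reply is that an effect of 1/3 is a planning value only for IS and VS. That is correct. For Preparation for Decision Making, 0.332 is a detectable effect, so the gain must be read with the smaller figures of Step 3.

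Finally, a reader might infer that the plan exceeds its own error limit, since 3 × 0.017 = 0.051. The documents do not support that either. The text prints 0.05/3 next to 0.017, so 0.017 is a display rounding. Even read literally, 0.051 is a worst-case bound: the family-wise error is 1 − (1 − 0.017)³ = 0.0501 with independent outcomes and below 0.049 at correlation 0.3. Positive correlation is plausible because two of the outcomes are subscales of one instrument.

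**Conclusion.** The point holds as a low-cost gain in efficiency. The current rule is valid and delivers its stated power. Holm controls the same 0.05 and rejects everything that Bonferroni at 0.05/3 rejects.

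At 190 per arm the gain is about 4 to 8 percentage points per outcome, and 10 to 20 points for showing all three. This rests on an effect of 1/3 on all three outcomes and on assumed correlations of 0 to 0.9. The gain shrinks to about 2 to 3 points on IS and VS if Preparation for Decision Making has no effect. It is nil for winning at least one outcome, and about nil if only one effect is real. None of this implies that the sample size is wrong or that type I error is uncontrolled.

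**What to change.** In Justification of Sample Size, replace the single-step rule with Holm, and state the same rule in the Analysis plan, which now has none. Suggested wording: *The three primary p-values will be ordered from smallest to largest and compared with 0.05/3, 0.05/2 and 0.05 in turn, stopping at the first that is not significant (Holm), so that the family-wise error is at most 0.05. The first step uses 0.05/3 unrounded. Confidence intervals at the Bonferroni level will be reported for each outcome.*

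This should be fixed before outcomes are compared by arm, since a step-down rule chosen after seeing results would not be credible.

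The cost is one or two sentences in each place. Sample size, data collection and follow-up are unchanged, and 190 per arm still gives 80.0% power at exactly 0.05/3. The one downside is that the intervals will not always agree with the Holm decisions: an outcome rejected at the second or third step can have a Bonferroni-level interval that includes zero. The report should say so.

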### **4.0 Research Plan and Methods**

The design for this study is a randomized trial with quitline patients recruited through state-based quitlines. Patients will be randomly assigned to the patient decision aid (200 patients) or standard educational information about lung cancer screening (200 patients). (Note that based on our estimates of attrition, up to 550 patients may be enrolled in the study to achieve a final sample of 400.) The design includes a pre-test assessment with a subscale of the knowledge measure developed for this study, an assessment at 1-week to collect data on the outcomes for the study and a 3-month follow-up to determine how well patients retain the information and track any use of screening services. A 6-month follow-up assessment will also be conducted on a subsample of the patients to track lung cancer screening rates via patient report.

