#### Allocation Strategy

Participants will be randomized at 1:1 ratio into Group A or B. Randomization will be stratified by states and by various block sizes. The randomization will be carried out via the Clinical Trial Conduct (CTC) website (<https://biostatistics.mdanderson.org/ClinicalTrialConduct>) which is housed on a secure server at MD Anderson and maintained by the MD Anderson Department of Biostatistics. Access to the website will be gained through usernames and passwords provided by the MD Anderson Department of Biostatistics. Training on the use of the CTC will be provided by the biostatistical collaborator of the study before the study activation.

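### The exploratory screening-rate comparison is sized on about 300 six-month completers, and the plan gives no way to use 3-month screening reports from patients without a 6-month report

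*Combined protocol and SAP*

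**What the plan says.** Section 2.0 treats completion of screening as exploratory and states no hypothesis about it in advance.

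Section 4.0 gives the enrolment figure, "up to 550 patients may be enrolled in the study to achieve a final sample of 400", and describes the last assessment: "A 6-month follow-up assessment will also be conducted on a subsample of the patients to track lung cancer screening rates via patient report". It gives no rule for choosing that subsample.

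Under the follow-up heading in Section 4.0, the same content is set for the 3-month and 6-month interviews: "we will repeat the knowledge measure and ask about any use of lung cancer screening services". The same text makes each later follow-up depend on the earlier ones having been completed.

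In Section 5.0, the Justification of Sample Size expects about 300 six-month completers: "We expect that approximately 300 participants will complete the 6-month follow-up assessment and provide information about completion of lung cancer screening (150/arm"). The power statement for them reads: "A two group chi-square test with a 0.05 two-sided significance level will have 83% power to detect the difference". The screening rates that this power figure assumes are given as "a ASR of 0.2 in Arm 2 and a ASR of 0.35 in Arm 1 (odds ratio of 2.154").

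The Analysis plan asks for a screening rate with a 95% confidence interval in each arm and then says: "Chi-square test will be used to assess the differences of the lung cancer screening rates between arms". It does not name the time point, the denominator, the handling of missing reports, or a rule for combining the two reports. Its intention-to-treat sentence refers to the primary scales and knowledge, and comes before the screening rate is mentioned.

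On allocation: "Participants will be randomized at 1:1 ratio into Group A or B", with randomisation stratified by state.

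**The concern.** By 6 months the trial will hold two kinds of screening information: reports at both 3 and 6 months from about 300 patients, and a 3-month report only from perhaps 100 to 140 more. The only denominator the plan attaches to the comparison is 150 per arm at 6 months. A two-by-two chi-square cannot take in someone followed only to 3 months. If that person reported a scan, the 6-month outcome is already known to be positive. If not, the person still informs the first 3 months.

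Two things are at stake. The first is precision, because the comparison as sized leaves usable information aside. The second is who is being compared. A 6-month report exists only for patients who were chosen for the subsample by an unstated rule and who had completed the earlier interviews after receiving their arm's materials. If completion is related to screening differently in the two arms, the completer comparison is distorted, and the plan has no analysis that would show it.

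**Working it through.** **1. The plan's own figure.** Inputs from the Justification of Sample Size: p2 = 0.20, p1 = 0.35, n = 150 per arm, two-sided alpha 0.05. The mean rate is 0.275.

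Power = Φ{[0.15 − 1.96·√(2·0.275·0.725/150)] / √[(0.20·0.80 + 0.35·0.65)/150]} = Φ{[0.15 − 1.96·0.05156]/0.05083} = Φ(0.963) = 0.832.

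The odds ratio is (0.35/0.65)/(0.20/0.80) = 2.154. Both stated figures reproduce.

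**2. Share of patients analysed.** 300/550 = 54.5% if all 550 enrol; 300/400 = 75% of the target final sample; 300/440 = 68% of the 440 implied by 80% retention of 550.

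**3. Precision available from both reports.** Assumptions: n3 = 200 per arm with a 3-month report (the target final sample), n6 = 150 per arm with a 6-month report, true 6-month rates 0.20 and 0.35, and a constant screening hazard. The documents give no figure for when scans occur.

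With h the probability of screening in each 3-month interval and S the proportion unscreened at 6 months, h = 1 − √S:
- Arm 2: h = 1 − √0.80 = 0.1056
- Arm 1: h = 1 − √0.65 = 0.1938

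Greenwood variance = S²·{h/[n3(1−h)] + h/[n6(1−h)(1−h)]}:
- Arm 2: 0.64·(0.000590 + 0.000880) = 0.000941
- Arm 1: 0.4225·(0.001202 + 0.001987) = 0.001347
- Sum: 0.002288

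Completer variance = 0.16/150 + 0.2275/150 = 0.002583.

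The ratio is 0.002288/0.002583 = 0.886, so effective n = 150/0.886 = 169 per arm. The power formula of step 1 then gives 87.4%. With n3 = 220 (80% of 275) the ratio is 0.855, effective n 176 and power 88.6%.

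**4. Sensitivity to timing.** The same variance form, with the assumed share of 6-month scans that occur by 3 months varied:

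| Share by 3 months | n3 per arm | Power |
|---|---|---|
| 10% | 200 | 83.9% |
| 20% | 200 | 84.6% |
| 30% | 200 | 85.4% |
| constant hazard (about half) | 200 | 87.4% |
| constant hazard | 220 | 88.6% |
| two-thirds | 220 | about 90% |

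**5. Events involved.** Under constant hazard, the 50 to 70 patients per arm with only a 3-month report would include about 5 to 7 known screens in Arm 2 (50·0.1056 to 70·0.1056) and about 10 to 14 in Arm 1 (50·0.1938 to 70·0.1938).

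**6. Exposure to selection (illustration only).** Suppose the true rate is 0.20 in both arms and, in one arm only, screened patients are r times as likely to complete 6 months as unscreened patients. The observed rate in that arm is 0.20r/(0.20r + 0.80). At r = 1.25 this is 0.238, and at r = 1.5 it is 0.273. The spurious difference is 3.8 to 7.3 points, against a planned difference of 15. The documents give no value for r.

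**The case against.** The strongest reply is that the count of 300 sits in a power statement, not in an analysis rule. The Analysis plan excludes nothing, and Section 4.0 gives tracking of screening use as one purpose of the 3-month interview. That stands: use of the 3-month reports is unspecified, not ruled out.

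It can also be said that the stakes are low. Screening is exploratory, the three primary outcomes are measured at 1 week, and the comparison already exceeds 80% power on the plan's assumptions. That also stands and sets the priority. The plan does, however, give this outcome a formal test and a power calculation, so its time point and denominator should be defined.

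Third, the 55% mixes a planned subsample with attrition. If the subsample is random or set by calendar date, that part need not bias anything. This is correct, but the plan specifies neither.

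Finally, the actuarial estimator does not remove selection. Patients with no 3-month report still contribute nothing: 550 − 440 = 110 to 550 − 400 = 150 of those enrolled. It also assumes non-informative censoring between 3 and 6 months. Both limits are real. A completer analysis, though, leaves out those same patients and also the ones with only a 3-month report, so it asks more of the missing data.

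**Conclusion.** The point holds as a modest, low-priority improvement. As sized, the screening comparison rests on six-month completers, and the plan has no rule for using 3-month reports from anyone else. Using both reports is worth about 4 power points under constant hazard with 200 per arm at 3 months (83% to 87%). Across the other timings and 3-month numbers tried, power is about 84% to 90%, a gain of roughly 1 to 7 points. These figures rest on the plan's rates of 0.20 and 0.35, on 150 per arm at 6 months, and on assumed timing of scans.

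Three stronger readings are not supported:
- **That the trial discards its 3-month screening data.** No sentence says so; the plan is silent on how they enter the test.
- **That the comparison is biased by arm.** The unstated subsample rule and the dependence on earlier interviews make bias possible. Nothing in the documents shows it or gives its size.
- **That the power statement is wrong.** It reproduces.

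**What to change.** In the Analysis plan:
- Define the outcome as cumulative screening by 6 months after randomisation.
- Estimate it in each arm with a discrete-time (actuarial) estimator and a 95% confidence interval, using all 3-month and 6-month reports. Count a positive 3-month report as an event, and censor at 3 months a patient whose only report is a negative one at 3 months.
- Do not simply add 3-month positives to the chi-square table. That would keep the events and drop the matching negatives, which inflates both rates.
- Compare arms with a state-stratified log-rank or discrete-time test, in line with the stratified randomisation.
- Report the 6-month completer chi-square as a sensitivity analysis.

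In Section 4.0, state how the 6-month subsample is chosen, by a rule independent of arm. One example is all patients randomised before a fixed calendar date, within the existing follow-up procedure.

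The cost is SAP wording, a sentence in Section 4.0 and a little programming, with no new data. The added assumption of non-informative censoring between 3 and 6 months should be stated. Contacting patients who missed earlier interviews would go further. It would change the follow-up procedure and add contacts and $25 payments, so it is not part of this recommendation.
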